## Statistical Plans

**Non-parametric and semi-parametric analyses.** The probabilities of CMV DNAemia, CMV DNAemia requiring pre-emptive therapy, CMV-D, NRM and relapse will be estimated by the cumulative incidence method (marginal probability).

Competing events will be defined as follows; in the case of relapse, the competing event was NRM without the occurrence of the disease. For CMV DNAemia, CMV DNAemia requiring pre-emptive therapy, CMV-D and GVHD the competing event will be relapse or death without the event. For NRM the competing event will be relapse.

The assumption of proportional hazards over time will be tested for all explanatory covariates using a time-dependent covariate. CMV DNAemia, CMV DNAemia requiring pre-emptive therapy and CMV-D will be treated as time-dependent co-variates.

If time-dependent covariates are to be included in the final model multivariate analyses of mortality the analysis will be performed by Cox proportional hazards regression model, with inclusion of those variables with a P value less than 0.1 in the prior univariate testing.

If either, early or late CMV DNAemia (included individually as time-dependent covariates) are found to have an impact on OS in the univariate analysis, semi-landmark plot will be constructed to illustrate visually the effect.

Statistical analysis of the clinical impact of CMV DNAemia at different periods of time before engraftment will be performed as described previously for early or late CMV DNAemia

All statistical analyses will be performed using SPSS version 20 (SPSS, Chicago, IL) and R version 2.12.2 (The CRAN project) with the packages survival v2.36-10, Design 2.3-0, prolim v1.2.1 and cmprsk v2.2-221.

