## Background and Rationale

Cytomegalovirus DNAemia occurs frequently in allogeneic hematopoietic stem cell transplant (allo-HSCT) recipients [1]. Both high-level and persistent virus DNAemia are known risk factors for CMV end-organ disease and perhaps non-relapse mortality [2]. CMV DNAemia is usually documented after engraftment, but it may occur before. The virological features and clinical consequences of these latter early-onset episodes remain largely unexplored. The U.S. Food and Drug Administration (FDA) has recently approved letermovir for prophylaxis of CMV infection and disease in adult CMV-seropositive allo-HSCT recipients (PREVYMIS™, Merck & Co., New Jersey, USA). In accordance with the design of the phase III, double-blind trial [3] the drug may be administered as early as the day of transplant and no later than 28 days post-transplant. Nevertheless, the timing of drug inception should be contingent on the clinical impact of very early episodes of CMV DNAemia. In a recent work from our group (single-center study) [4] we found that a total 38 out of the 197 patients in our series developed CMV DNAemia before engraftment (cumulative incidence, 19%; 95% CI, 10-30.3%). Nine episodes of CMV DNAemia were detected prior to the time of donor progenitor cell infusion. A greater number of post-engraftment episodes required preemptive antiviral therapy compared with pre-engraftment episodes (62.5% vs 44.7%;  $P=0.05$ ). The cellular content of the donor progenitor cell infusion and transplant characteristics of patients did not differ between patients with pre- or post-engraftment CMV DNAemia. The cumulative incidence of overall mortality by days 100 and 365, aGVHD by day 100 and relapse by day 365 were not significantly different between patients with pre-engraftment or post-engraftment CMV DNAemia. Our study was limited by the retrospective and single-center design and the scarce number of pre-engraftment CMV DNAemia episodes included; therefore, the results may not be extrapolated to other transplantation centers or patient cohorts. Further retrospective and prospective studies are thus required to validate the data presented herein.

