## Objectives

**1. Assess the incidence of pre-engraftment CMV DNAemia using highly sensitive real-time PCR assays in allo-HSCT**

**2. Evaluate its impact of pre-engraftment CMV DNAemia on the time to engraftment, overall mortality, and non-relapse mortality.**

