**Inclusion criteria include:**

- Recipients >18 years old
- CMV seropositive recipients and/or donors
- DNA load monitoring by real-time PCR starting from day -7 and conducted on a weekly CMV basis (0, +7, +14,...) at least until day +100
- First allo-HSCT
- T-cell replete allograft

Essential variables which include patients, donor and transplant's characteristics as well as post-transplant outcome will be retrieved from MED-A of PROMISE EBMT database.

Specific CMV data (including one-year longitudinal PCR results, date of onset and type of pre-emptive antiviral therapy as well as CMV disease data) will be retrospectively reported by each participating center.

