**Analysis of the clinical impact of CMV DNAemia will be performed by evaluation of:**

- Time to engraftment
- Overall mortality

The analysis will be performed comparing the clinical impact of CMV DNAemia as described before, in relation to time of CMV DNAemia initiation in the following groups:

- Patients with DNAemia before engraftment vs after engraftment
- Patients with DNAemia before engraftment and before HSC infusion vs patients with DNAemia before engraftment after HCS infusion
- Comparison of time of initiation of CMV DNAemia from day -7 to HCS infusion on a weekly basis until engraftment.

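### Does the lack of a stated rule for engraftment put the incidence of pre-engraftment CMV DNAemia (Objective 1) at risk?

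*Combined protocol and SAP*

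**What the plan says.** The first item under Objectives reads: "Assess the incidence of pre-engraftment CMV DNAemia using highly sensitive real-time PCR assays in allo-HSCT". Statistical Plans then lists what will be estimated: "The probabilities of CMV DNAemia, CMV DNAemia requiring pre-emptive therapy, CMV-D, NRM and relapse will be estimated by the cumulative incidence method". The DNAemia entry there is not restricted to the period before engraftment. The matching competing-event rule is "For CMV DNAemia, CMV DNAemia requiring pre-emptive therapy, CMV-D and GVHD the competing event will be relapse or death without the event".

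Three other places bear on the point:

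- The inclusion criteria require PCR monitoring "starting from day -7 and conducted on a weekly CMV basis (0, +7, +14,...) at least until day +100", so sampling continues well past engraftment.
- The section on clinical impact plans a "Comparison of time of initiation of CMV DNAemia from day -7 to HCS infusion on a weekly basis until engraftment". This shows the intended window, but for outcome comparisons, not for incidence.
- Statistical Plans mentions the pre-engraftment periods once more: "Statistical analysis of the clinical impact of CMV DNAemia at different periods of time before engraftment will be performed as described previously". That too concerns clinical impact.

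Nowhere is engraftment without DNAemia called a competing event, a censoring event or a non-event. Statistical Plans states neither a time origin nor a reporting day for the incidence.

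**The concern.** A patient can have pre-engraftment DNAemia only until engraftment, and most patients leave that period by engrafting. A competing-event rule that names only relapse and death therefore seems to omit the main one. Applied to Objective 1, it could be read in three ways:

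1. Count any DNAemia up to some day, including episodes after engraftment.
2. Count pre-engraftment episodes and censor DNAemia-free patients at engraftment.
3. Count pre-engraftment episodes and keep engrafted, DNAemia-free patients in the denominator as event-free.

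Reading 1 answers a different question. Reading 2 estimates the risk as if engraftment never happened. Both rise with the reporting day. If either were used, the first objective would be answered with an inflated figure, and the comparison with the earlier single-centre result would be spoiled.

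**Working it through.** **The documents' own figure.** Background and Rationale reports that "a total 38 out of the 197 patients in our series developed CMV DNAemia before engraftment", with a cumulative incidence of 19%. The crude proportion is 38/197 = 0.193, which reproduces it. Censoring at engraftment would normally give a higher value, so the earlier figure fits reading 3 or engraftment as a competing event.

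**Reading 3 against an explicit competing event.** Let N patients be followed from day -7, and let D of them have DNAemia before engraftment, relapse or death. If nobody is lost before the last pre-engraftment event, the cumulative incidence at its plateau is D/N. It makes no difference whether engrafted patients are removed through a competing event or kept as non-events, because neither choice alters D or N. Monitoring to at least day +100 is an entry condition, so early loss should be negligible. On the earlier data both give 38/197 = 19.3%. At N = 878 that is 0.193 × 878 ≈ 169 patients.

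**What the other readings would cost.** The documents give no engraftment times and no DNAemia hazard, so these are assumptions: constant hazard h from day -7, lognormal engraftment time (log-SD 0.25), about 3% relapse or death before engraftment, and h set so that 19.3% have DNAemia before engraftment. Results from 400,000 simulated patients per row:

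| Assumed median engraftment | h per day | Competing event, plateau | Competing event, day +28 | Censored, day +28 | Any DNAemia, day +28 | Censored, day +42 |
|---|---|---|---|---|---|---|
| day 12 | 0.01132 | 19.3% | 19.3% | 33.1% | 31.9% | 42.3% |
| day 16 | 0.00932 | 19.3% | 19.3% | 27.1% | 27.2% | 34.9% |
| day 20 | 0.00792 | 19.3% | 19.1% | 23.8% | 23.8% | 29.9% |
| day 24 | 0.00687 | 19.3% | 18.6% | 21.1% | 21.1% | 28.2% |

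A hand check, ignoring relapse and death: the censored value at day +28 is about 1 − exp(−35h). For h = 0.00932 this is 1 − exp(−0.326) = 27.8%, against 27.1% simulated.

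A second simulation used weekly sampling, 9/197 = 4.6% positive before infusion, engraftment medians of 14 to 20 days with SD 3 or 6, and per-sample risk falling, constant or rising. Censoring gave 22% to 41% at day 28 and 21% to 32% at day 21; the upper ends need rising risk and early engraftment.

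For scale, the binomial 95% half-width at N = 878 is 1.96 × √(0.193 × 0.807 / 878) = 2.6 percentage points. Most of the errors above exceed it; the smallest day-21 error, about 1.3 points, does not.

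**Does the text lead to reading 1 or 2?**

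- Reading 1 contradicts Objective 1, which is limited to episodes before engraftment. Counting all DNAemia is the proper estimate of overall DNAemia, which Statistical Plans lists separately.
- Reading 2 needs an act of censoring that no section mentions, in a plan that commits to cumulative incidence methods.
- Reading 3 is what results when the Objective 1 event is put into the existing relapse-or-death rule with nothing added.

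**The case for a change.** The strongest case for a change is that a plan should not rely on the analyst choosing correctly. Incidence before engraftment is the first objective, its endpoint is not defined in Statistical Plans, and the unmentioned event is the most common way out of the risk period. At least 10 centres contribute data, so comparability with the single-centre result depends on consistent handling. A clarification would take one or two sentences and need no new data: PCR results and time to engraftment are already collected, and a competing-risks package is already listed.

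The agreement between 19% and 38/197 is also only indirect evidence of practice. Statistical Plans does not adopt the earlier method, and the reported interval of 10% to 30.3% does not follow from 38/197 (Wald 13.8% to 24.8%, Wilson 14.4% to 25.4%, Clopper-Pearson 14.0% to 25.5%).

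Much of this stands as description. The omission is real, the direction of the possible bias is clear, and neither a definition of engraftment nor a reporting day is written down. It does not show that any stated rule is wrong. The relapse-or-death rule is sound for overall DNAemia and gives the right plateau for Objective 1 when the event is taken as worded. The inflation requires a mistake that the plan does not ask for, and its size rests on assumptions from outside the documents.

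**Conclusion.** No change is needed. Statistical Plans leaves the Objective 1 endpoint unwritten, but Objective 1 limits the event to the period before engraftment, and the planned cumulative incidence method then keeps engrafted patients as event-free. With follow-up complete through engraftment, that equals the competing-event estimate: 19.3% if the earlier proportion holds. Values of roughly 21% to 33% at day +28 (constant hazard, median engraftment day 12 to 24), or 22% to 41% across wider risk shapes, arise only if an analyst censors at engraftment; counting later episodes has a similar effect. Nothing in the plan calls for either. Spelling out the endpoint would be tidy, but would not alter the figure a sensible analysis produces. This rests on two conditions: monitoring that is complete to engraftment, which the entry criteria support, and reporting the incidence once essentially all patients have engrafted.

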NCT number	NAV-CMV-2019
Date	May, 2018
Study Title:	Pre-engraftment Cytomegalovirus DNAemia in allogeneic hematopoietic stem cell transplant recipients: incidence, risk factors and clinical outcomes
Request Date:	
Principal Investigator Contact Information	[name]
Name:	[name]
Title:	MD, PhD
Address 1	[name]
Address 2	
City, ST, Zip	[name]
Phone/Fax:	[name]
[contact]	
Institution Contact Information	INCLIVA, Institución de Investigación Sanitaria, Hospital Clínico de Valencia
Name:	INCLIVA, Institución de Investigación Sanitaria, Hospital Clínico de Valencia
Address 1	[name]
Address 2	
City, ST, Zip	[name]
Phone/Fax:	[name]
website	
Number of Subjects: 878	

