### **Hypothesis**

**Very early episodes of CMV DNAemia have no impact on the occurrence of engraftment, overall mortality and non-relapse mortality.**

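### The P<0.1 entry rule can put CMV DNAemia, its therapy-requiring subset and CMV disease into one mortality model, where the DNAemia hazard ratio no longer measures the impact named in objective 2

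*Combined protocol and SAP*

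**What the plan says.** All references are to the combined protocol and SAP.

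- **Objectives**, second item: "Evaluate its impact of pre-engraftment CMV DNAemia on the time to engraftment, overall mortality, and non-relapse mortality".
- The answer that the plan expects, given under **Hypothesis**, is this: "Very early episodes of CMV DNAemia have no impact on the occurrence of engraftment, overall mortality and non-relapse mortality".
- **Statistical Plans**, coding of the CMV variables: "CMV DNAemia, CMV DNAemia requiring pre-emptive therapy and CMV-D will be treated as time-dependent co-variates".
- **Statistical Plans**, multivariate model: it is conditional, "If time-dependent covariates are to be included in the final model multivariate analyses of mortality", and is then a Cox model built "with inclusion of those variables with a P value less than 0.1 in the prior univariate testing". This is the only entry rule given.
- **Statistical Plans**, plot: "If either, early or late CMV DNAemia (included individually as time-dependent covariates) are found to have an impact on OS in the univariate analysis", a semi-landmark plot follows. This is the only wording about separate entry. It covers early and late DNAemia at the univariate step and mentions neither therapy-requiring DNAemia nor CMV disease.

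The section names no exposure that is always retained, bars no variable, and does not say whether a total or a direct effect is wanted.

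**The concern.** The three CMV variables are not parallel risk factors. DNAemia requiring pre-emptive therapy is by definition a subset of DNAemia. CMV disease lies downstream of it: Background and Rationale itself counts high or lasting viral load among the risk factors for end-organ disease.

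If all three pass the P<0.1 screen and enter together, the effect of DNAemia is split across three coefficients. The one labelled DNAemia then refers to episodes with no therapy need and no CMV disease. Objective 2 asks for the impact of pre-engraftment DNAemia on mortality, which reads as a total effect.

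The stated hypothesis is one of no impact and the plan gives no equivalence margin. A DNAemia coefficient that is near 1, or merely imprecise, could therefore be taken as confirmation when it answers a different question.

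**Working it through.** **Figures from the documents**

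- Pre-engraftment DNAemia in the earlier single-center series: "38 out of the 197 patients in our series developed CMV DNAemia before engraftment". 38/197 = 19.3%, which agrees with the stated 19%.
- Share of episodes needing pre-emptive therapy: 44.7% before engraftment, 62.5% after (Background and Rationale).
- Sample size: "Number of Subjects: 878". The documents give no derivation, so it cannot be reproduced. It implies about 878 × 38/197 = 169 pre-engraftment episodes, of which 169.4 × 0.447 ≈ 76 would need therapy.

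**Assumptions, not in the documents:** about 30% one-year baseline mortality; CMV disease in 15% of therapy-requiring and 3% of other episodes; onset times; and the true HRs below. The simulated exposure has the pre-engraftment prevalence (19.3%) and therapy share (44.7%), and the reference is no DNAemia.

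**Step 1: what the coefficient means.** Let d be the direct HR of DNAemia, t the further factor for therapy need and c the further factor for CMV disease. The joint model estimates d. With therapy share s = 0.447, and ignoring onset delays and attrition, the total HR is roughly

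d × [(1 − s)(1 + 0.03(c − 1)) + s × t × (1 + 0.15(c − 1))].

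For d = 1, t = 1.5, c = 3 this is 0.553 × 1.06 + 0.447 × 1.5 × 1.30 = 0.586 + 0.872 = 1.46, while the joint model targets 1.0. For d = 1.5, t = 0.6, c = 1 it is 1.5 × (0.553 + 0.447 × 0.6) = 1.23, while the joint model targets 1.5.

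**Step 2: large-sample check.** Cox models with time-dependent covariates, 60,000 simulated patients per scenario:

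| Scenario (d, t, c) | Rough total HR, step 1 | DNAemia alone | Joint model |
|---|---|---|---|
| Fully mediated (1.0, 1.5, 3) | 1.46 | 1.35 | 1.01 |
| Partly mediated (1.2, 1.3, 2) | 1.49 | 1.46 | 1.20 |
| All direct (1.5, 1, 1) | 1.50 | 1.49 | 1.50 |
| Mixed (1.3, 0.7, 3) | 1.29 | 1.26 | 1.30 |
| Lower hazard if treated (1.5, 0.6, 1) | 1.23 | 1.21 | 1.51 |

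The hand formula agrees only roughly, as expected. The joint column recovers d in every row; the DNAemia-alone column is the total effect.

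**Step 3: the P<0.1 rule applied at N = 878**, 500 replicates per scenario. Results are for replicates in which DNAemia entered with at least one downstream variable:

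| Scenario | Share with such entry | Mean HR, alone to joint | P<0.05 for DNAemia, alone to joint | SE ratio |
|---|---|---|---|---|
| Fully mediated | 62% | 1.45 to 1.08 | 80% to 4% | 1.38 |
| Partly mediated | 78% | 1.51 to 1.25 | 89% to 22% | 1.32 |
| All direct | 59% | 1.60 to 1.48 | 97% to 60% | 1.26 |
| Mixed | 38% | 1.42 to 1.30 | 81% to 22% | 1.12 |
| Lower hazard if treated | 6% | 1.43 to 1.49 | 77% to 53% | 1.12 |

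These rows are selected on P<0.1, so the DNAemia-alone HRs and significance rates are inflated. The last row rests on about 30 replicates. The same rule can also drop the exposure: in the fully mediated scenario DNAemia failed to enter in 38% of replicates.

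**Step 4: why precision falls.** For DNAemia with prevalence p = 0.193 and a nested subset of share s, both treated as fixed covariates, R² = s(1 − p)/(1 − ps). At s = 0.447, R² = 0.395 and the variance inflation factor is 1/(1 − 0.395) = 1.65. At s = 0.625, R² = 0.574 and the factor is 2.35. The square roots, 1.28 and 1.53, are of the same order as the simulated SE ratios.

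**The case against.** The strongest reply is that the plan never says the three variables share a model. Calling them time-dependent describes their coding, the multivariate Cox model is conditional, and each variable must first pass the screen. This stands in part: a reader might infer that the plan commits to joint entry, and it does not. But the rule admits whatever passes, and the wording about individual inclusion does not reach the multivariate step or the two downstream variables.

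A second reply concerns direction. A reader might infer that the rule necessarily pulls the HR to the null and so favours the hypothesis. The documents do not support that, because they give no mortality hazard by therapy status or CMV disease. Steps 2 and 3 show movement toward the null, none, or away from it, depending on what is assumed.

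Third, univariate testing comes first, so an estimate for DNAemia free of the downstream variables will exist. That is correct, and the information is not lost: the DNAemia and therapy coefficients together still describe therapy-requiring episodes. However, the univariate estimate is unadjusted for baseline confounders, and no planned model gives an adjusted total effect whenever a downstream variable enters.

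Fourth, the first group comparison under Study Design/Clinical Plan is DNAemia before versus after engraftment, and the HRs here do not apply to it. For illustration, take hazards of 1.0 without and 2.0 with therapy need, relative to no DNAemia. The averages are 0.553 + 0.447 × 2 = 1.45 for early and 0.375 + 0.625 × 2 = 1.63 for late episodes, a ratio of 0.89. Adjustment would move that ratio toward 1 by removing an apparent advantage of early episodes, not by hiding harm. This also stands.

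**Conclusion.** The point holds as a defect in the selection rule. Followed literally, the rule can put DNAemia, its nested subset and its consequence in one mortality model. Once that happens, the DNAemia coefficient is not the quantity in objective 2. That change of meaning follows from how the variables are defined, and no assumed effect size is needed for it.

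The loss of precision appeared in all five N = 878 scenarios (SE ratio 1.12 to 1.38). The HR shifts are illustrative: they rest on the assumed mortality, CMV disease rates, onset times and hazards, and they concern DNAemia versus none only. A bias toward the no-impact hypothesis may be claimed only for the case where harm runs through therapy-requiring DNAemia or CMV disease. The documents do not show whether that case applies, so neither size nor direction in the real data can be stated.

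**What to change.** Add to Statistical Plans: the primary mortality model always retains early and late CMV DNAemia as time-dependent covariates and adjusts for baseline covariates only; DNAemia requiring pre-emptive therapy and CMV disease do not enter that model, whatever their univariate P value. Analyse each of those two as an exposure in its own model, or show a joint model labelled as a secondary, mediation-type analysis.

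The cost is one sentence in the plan and a few extra model runs. No new data are needed, since PCR results, start of pre-emptive therapy and CMV disease are already to be reported by the centers.

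### The univariate P<0.1 screen also applies to pre-engraftment DNAemia, the exposure under study: if its true crude hazard ratio for overall mortality is 1, the plan gives no adjusted estimate 90% of the time

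*Combined protocol and SAP*

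**What the plan says.** The second objective is: "Evaluate its impact of pre-engraftment CMV DNAemia on the time to engraftment, overall mortality, and non-relapse mortality". The Hypothesis section expects that very early episodes "have no impact on the occurrence of engraftment, overall mortality and non-relapse mortality".

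In Statistical Plans, "CMV DNAemia, CMV DNAemia requiring pre-emptive therapy and CMV-D will be treated as time-dependent co-variates". When time-dependent covariates enter the final mortality model, that model is a Cox regression "with inclusion of those variables with a P value less than 0.1 in the prior univariate testing". The paragraph after it has early and late DNAemia entered one at a time in the univariate analysis of overall survival, and draws a semi-landmark plot only if one of them shows an effect there. The section then sends the periods before engraftment to the same analysis as early and late DNAemia.

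Study Design/Clinical Plan asks for the comparison "Patients with DNAemia before engraftment vs after engraftment". It also says that "Essential variables which include patients, donor and transplant's characteristics" will be taken from the MED-A form of the transplant registry. The plan does not list which of these are confounders to adjust for.

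**The concern.** Screening by univariate P is a common, if weak, way to choose adjustment covariates. Here the list being screened includes the exposure itself. Early DNAemia is tested univariately against overall survival, the screen decides what enters the adjusted model, and no text keeps early DNAemia in regardless.

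The screen therefore works against the study's own question. The closer the crude HR is to 1, the more likely the exposure is dropped and the adjusted estimate is never produced. In a retrospective cohort a crude HR near 1 need not mean an adjusted HR near 1, because confounding can mask an effect. The adjusted HR and its interval are what a claim of no impact needs, and the plan omits them most often when that claim appears to be true.

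The confounders pass through the same screen, so the adjustment set is also left to the data.

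**Working it through.** **Figures in the plan.** The documents give no power, death count, detectable HR or derivation of the sample size, so there is no design figure to reproduce. The only operating figure is the 0.1 threshold, taken here as two-sided because sidedness is not stated.

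**True crude HR of 1.** Under the null the P value is uniform, so P(screened out) = 1 - 0.10 = 0.90. This needs no assumption about deaths, exposure share or sample size. A simulation of a time-dependent exposure (4,000 runs, 878 patients, 19% exposed, assumed 30% one-year mortality) gave 0.901.

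**True crude HR above 1 (illustration).** Inputs:
- N: "Number of Subjects: 878" (title table).
- Exposed share p: "38 out of the 197 patients in our series developed CMV DNAemia before engraftment" (Background and Rationale), so p = 38/197 = 0.193.
- Mortality: not in the documents; assumed 25-40%, so D = 878 × 0.25 = 219.5 to 878 × 0.40 = 351.2 deaths.

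SE of the log HR, early versus all others = 1/√(D·p·(1-p)):
- 25% mortality: 1/√34.17 = 0.171
- 40% mortality: 1/√54.68 = 0.135

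P(screened out) = Φ(1.645 - ln HR/SE) - Φ(-1.645 - ln HR/SE):

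| True crude HR | 25% mortality | 40% mortality |
|---|---|---|
| 1.0 | 90% | 90% |
| 1.2 | 72% | 62% |
| 1.3 | 54% | 38% |
| 1.5 | 23% | 9% |

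For HR 1.3 at 25% mortality, ln 1.3/0.171 = 1.534, and Φ(0.111) - Φ(-3.179) = 0.544 - 0.001 = 0.54.

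Across the pilot's interval for the exposed share (10-30.3%), the HR 1.3 figure runs from 68% (10% exposed, 25% mortality) to 27% (30.3% exposed, 40% mortality). The formula is approximate. At HR 1.5 and an assumed 30% mortality it gives 17.5% (19% exposed), against 12.6% in the simulation, where the 30% applied to the unexposed and the exposed died more often. The non-null figures show the order of size only.

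**Precision after the fix, at HR 1.** The 95% interval is exp(±1.96·SE). Adjustment divides SE by √(1-R²), where R² is the share of exposure explained by covariates, assumed to be 0.10. With separate early and late terms, SE = √(1/D_early + 1/D_comparator)/√(1-R²). This assumes 40% late DNAemia and equal mortality in each state, and allocates deaths by final DNAemia state.

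| Contrast | 25% mortality | 40% mortality |
|---|---|---|
| Early vs all others, crude | 0.72-1.40 | 0.77-1.30 |
| Early vs all others, adjusted | 0.70-1.42 | 0.76-1.32 |
| Early vs none, or early vs late, adjusted | 0.68-1.47 | 0.74-1.36 |

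For the last row at 25% mortality, D_early = 42.3 and D_none = 89.4, so SE = 0.187/√0.9 = 0.197. Against the crude 0.171 that is a ratio of 1.15, or about 15% wider on the log scale. The ratio is the same at 40% mortality.

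**The case against.** **The wording is loose.** The sentence opens with a condition about time-dependent covariates being in the final model. It could be read as taking DNAemia as given and screening only the other variables around it. That reading is possible, but the text does not say it, and the next paragraph places early DNAemia in the univariate step. If it is what the authors meant, the fix records it.

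**The 90% is not specific to this trial.** True: it holds for any null variable at this threshold. It matters here because the variable is the exposure and its expected effect is null. It refers to the true crude HR; an observed crude HR of exactly 1 would never pass.

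Stronger readings that the documents do not support:
- *The plan yields no mortality estimate at all.* A crude time-dependent HR with its interval stays obtainable, and an adjusted model could be fitted later, though not as the planned analysis. What is lost is planned adjustment.
- *The screen is why a no-impact finding could hide a substantially raised hazard.* The width of the interval comes from the number of deaths. At the same point estimate, forcing the exposure into an adjusted model gives an equal or wider interval.
- *The reported adjusted HR will be exaggerated by a known amount when the exposure passes.* Only the crude estimate, conditional on passing, can be worked out from these inputs; the adjusted one was not evaluated.
- *All objectives are affected.* Incidence and time to engraftment are not touched by this rule.

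**Conclusion.** The concern holds for overall mortality. Followed as written, the plan omits an adjusted HR for early DNAemia 90% of the time when its true crude HR is 1. That figure rests on the 0.1 threshold alone, for a single univariate test that holds its nominal level. The figures at HR 1.3 (54-38%) and 1.5 (23-9%) are illustrations that depend on the assumed 25-40% mortality and the pilot's exposure share.

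The sub-periods before engraftment appear to inherit the rule, because Statistical Plans sends them to the same analysis as early and late DNAemia. Whether the word mortality in the rule also covers non-relapse mortality is not stated, so no claim is made there.

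This should be fixed before analysis. It is a gap in the planned estimate and does not show that the study's conclusion would be wrong. The documents give no basis for sizing the confounding bias that adjustment would remove.

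**What to change.** In Statistical Plans:

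1. State that early and late DNAemia stay in the adjusted overall-mortality Cox model as time-dependent covariates whatever their univariate P. Keeping late DNAemia allows the before-versus-after-engraftment comparison in Study Design/Clinical Plan to be estimated from the same model.
2. Name in advance the pre-transplant patient, donor and transplant characteristics to adjust for, chosen from the MED-A retrieval, and include them regardless of P.
3. Report the adjusted HRs with 95% intervals.
4. Handle the sub-periods before engraftment the same way, and say whether the mortality rule extends to non-relapse mortality.

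The first change takes the chance of having no adjusted estimate from 90% to 0 at a true crude HR of 1.

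The cost is SAP wording, with no new patients and no data beyond what is already to be retrieved, plus the loss of precision shown in the second table. Adjustment alone costs little. Most of the roughly 15% widening comes from splitting the comparator into no DNAemia and late DNAemia.
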